Research Repositories: If the purpose of this submission is to establish a Research Repository (bank, registryou plan to collect is already available from a commercial supplier, clinical lab, or established IRB approved research repository, provide scientific justification for establishing an additional repository collecting duplicate material. Describe the repository design and operating procedures. For relevant information to include, see the UK Research Biospecimen Bank Guidance or the UK Research Registry Guidance.

The proposed study is a two staged prospective study comparing skin closure with octyl-2-cyanoacrylate (Dermabond) with conventional non-absorbable sutures in the direct excision brow lift.

In stage 1, subjects will be consented to receive one of two surgical closing techniques on a bilateral brow ptosis repair: 1) deep dermal sutures and superficial interrupted sutures (the standard of care at the University of Kentucky); or 2) deep dermal sutures and octyl-2-cyanoacrylate skin glue application for superficial closing. Subjects will undergo a single closing technique on both sides. Four subjects will complete surgery in each arm (n=8 subjects total: n=4 for arm 1, and n=4 for arm 2). After the follow-up period, the scar appearance between groups will be compared. If there the octyl-2-cyanoacrylate (dermabond) group have worse appearing scars, then we will not continue to study. If the difference in appearance is negligible, then we will return to the IRB for approval to advance to stage two.

Stage two is outlined below:

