Each patient will serve as their own control, with one brow undergoing skin closure with interrupted 6-0 prolene suture and the other with octyl-2-cyanoacrylate skin glue. Deep dermal sutures will placed in both wounds at 1 cm intervals. The patients will be randomized as to which side receives what type of closure (i.e. the right side receiving skin glue and the left receiving skin sutures or vice versa). This will prevent acquired bias during the scar analysis. The operation is done under monitored anesthesia care. We will record the time it takes to close both wounds. We will determine the precise costs of the skin glue and suture and the incurred costs per minute of operating room time. We will monitor the patients after discharge for any complications (infection, wound dehiscence, skin reaction, etc), which will be recorded. Patients will follow up at 10 days, and 3 months. Photos will be taken at the follow up visits with patient's consent. The scars will be aesthetically analyzed by plastic surgeons in terms of which scar is more aesthetically pleasing. In addition, the patient and observer (physician) will analyze the scar using the well established Patient and Observer Scar Assessment Scale. The physicians completing the forms are the research personnel.

Attachments

Subject Recruitment Methods & Advertising

Describe how the study team will identify and recruit subjects. Please consider the following items and provide additional information as needed so that the IRB can follow each step of the recruitment process.

- How will the study team identify potential participants?
- · Who will first contact the potential subjects, and how?
- Will you use advertisements? If so, how will you distribute those?
- How and where will the research team meet with potential participants?
- If applicable, describe proposed outreach programs for recruiting women, minorities, or disparate populations.
- How you will minimize undue influence in recruitment?
- · Attach copies of all recruiting and advertising materials (emails, verbal scripts, flyers, posts, messages, etc.).

For additional information on recruiting and advertising:

- IRB Application Instructions Advertisements
- PI Guide to Identification and Recruitment of Human Subjects for Research

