Informed consent will be obtained prior to enrollment in the study. The patient will undergo thorough history and physical examination in the clinic setting. We will then schedule for surgery if all criteria are met. The anesthesia staff will administer the standard and appropriate anesthetic. Local anesthesia will be administered. For step one of this research project the surgical procedure will be identical for all patients except the final superficial skin closure. We will design the amount of upper lateral superior brow tissue requiring excision to correct the patient's ptosis. Calipers will be used to ensure precise measurements. We will use a 15 blade to incise through the skin to the level of the frontalis muscle and fascia on both sides. Hemostasis will be achieved with Bovie electrocautery over the wounds. Both brows will be closed with 5-0 Vicryl in the subcutaneous and deep dermal layers spaced at 1 cm apart. The skin layer will be closed using interrupted 6-0 prolene sutures or with octyl-2-cyanoacrylate bilaterally. Patients will be randomized into either group. Photos will be taken both before the procedure and afterwards for research purposes. Then an independent group will evaluate photos and scar surveys for acceptability of results. The group will prepare a summary report. The photos and the summary report will be submitted to the IRB. If the the 6-0 prolene closure technique and octyl-2-cyanoacrylate closure technique are deemed to be equivocal, a request to move to Phase 2 will be made.

In phase 2 of the research project, a group of patients will all undergo the same procedure but each patient will be their own control. One side will be closed with interrupted 6-0 proline sutures and the other side closed with octyl-2-cyanoacrylate, it will be randomized what side will get which superficial skin closure.

Attachments

Data Collection & Research Materials

In this section, please provide the following:

- Describe all sources or methods for obtaining research materials about or from living individuals (such as specimens, records, surveys, interviews, participant observation, etc.), and explain why this information is needed to conduct the study.
- For each source or method described, please list or attach all data to be collected (such as genetic information, interview scripts, survey tools, data collection forms for existing data, etc.).

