Both skin closure techniques involved in the study are consistent with the current standard of care. We are comparing two techniques commonly used by practicing surgeons. Because the surgeon could select either closure technique in the operation in a non- research setting, these are not considered additional costs.

Data and Safety Monitoring

The IRB requires review and approval of data and safety monitoring plans for greater than minimal risk research or NIH-funded/FDA-regulated clinical investigations.

- If you are conducting greater than minimal risk research, or your clinical investigation is NIH-funded, describe your Data and Safety Monitoring Plan (DSMP). Click here for additional guidance on developing a Data and Safety Monitoring Plan.
- If this is a non-sponsored investigator-initiated protocol considered greater than minimal risk research, and if you are planning on using a Data and Safety Monitoring Board (DSMB) as part of your DSMP, click here for additional guidance for information to include with your IRB application.

We will institute a data monitoring and safety plan. To mitigate and detect harm, the patient will be seen the week after surgery and again at six weeks. At these follow up visits, the PI will assess the subjects for any adverse events. The PI will assess for wound dehiscence, signs of infection, and necrosis. In addition, the patients will have access to the emergency contact information of [name]. The PI will be the sole monitor of the clinical investigation. Conflict of interest will be mitigated by comparing the surgeon's scar survey score to the patient's scar survey score. An independent group comprised of two or more non Study Personnel will review before/after photographs and scar surveys for acceptability. These photos and scar surveys will be stripped of identifiers prior to any non-study personnel reviewing. The group will prepare a summary report that will be submitted to the IRB.

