If a significant discrepancy is apparent, we will not proceed onto the phase two. Toward this end, phase one of the protocol will investigate the scar phenotype of Dermabond closed wounds in a bilateral fashion so as to ascertain if there will be a significant difference between Dermabond and suture closed wounds. The results of phase 1 will be reported to the IRB after each datapoint is collected and the IRB will help decide if the study will proceed. We will not report events to any other entities besides the University of Kentucky ORI IRB. Any instance of wound dehiscence, necrosis or serious infection in the Dermabond group will be criteria for temporary suspension of the study. The development of any of these adverse effects in the superficial suture group will not result in study suspension.

Back to Top

Future Use and Sharing of Material (e.g., Data/Specimens/Information)

If the material collected for this study will be used by members of the research team or shared with other researchers for future studies, please address the following:

- list the biological specimens and/or information that will be kept
- · briefly describe the types, categories and/or purposes of the future research
- · describe any risks of the additional use
- · describe privacy/confidentiality protections that will be put into place
- describe the period of time specimens/information may be used
- describe procedures for sharing specimens/information with secondary researchers
- · describe the process for, and limitations to, withdrawal of specimens/data

Are you recruiting or expect to enroll **Non-English Speaking Subjects or Subjects from a Foreign Culture**? (does not include short form use for incidentally encountered non-English subjects)

∩ Yes ∩ No

Non-English Speaking Subjects or Subjects from a Foreign Culture

Recruitment and Consent:

Describe how information about the study will be communicated to potential subjects appropriate for their culture, and if necessary, how new information about the research may be relayed to subjects during the study.

When recruiting Non-English-speaking subjects, provide a consent document in the subject's primary language. After saving this section, attach both the English and translated consent documents in the "Informed Consent" section.

Cultural and Language Consultants:

The PI is required to identify someone who is willing to serve as the cultural consultant to the IRB.

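### Do the unnamed visit for the stage 1 scar comparison and the unnamed POSAS visit in the SAP call for a change to the plan?

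*Combined protocol and SAP*

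**What the plan says.** For stage 1, Study Design fixes the order of events but not the date: "After the follow-up period, the scar appearance between groups will be compared". The text then turns to the next stage ("Stage two is outlined below"), and the first visit schedule appears inside that outline: "Patients will follow up at 10 days, and 3 months". The same outline ties photographs to the follow-up visits and describes the POSAS ratings.

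Research Procedures covers stage 1 photographs without a day or visit: "Photos will be taken both before the procedure and afterwards for research purposes". The independent assessment follows, also undated: "Then an independent group will evaluate photos and scar surveys for acceptability of results".

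Data and Safety Monitoring gives a second set of visits, with no stage named: "the patient will be seen the week after surgery and again at six weeks". It assigns those visits to the investigator's check for adverse events. It repeats the independent review ("An independent group comprised of two or more non Study Personnel will review before/after photographs and scar surveys for acceptability") and adds running reports: "The results of phase 1 will be reported to the IRB after each datapoint is collected and the IRB will help decide" whether the study goes on.

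The inclusion criteria require patients to attend at set intervals but do not list them. The SAP, dated March 30, 2025, is a short paragraph. It uses only the patient POSAS from post-operative visits, in the plural, plus demographic data, and describes the analysis in the past tense as basic descriptive statistics.

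**The concern.** Scar appearance is the second objective, and it decides whether stage two is requested. Early and later ratings of a scar need not agree, so a reader wants to know how old the scars were when the two closures were compared. The text offers a later visit at six weeks in one place and at 3 months in another, does not relate them, and assigns neither to stage 1 scar rating. Reporting to the IRB after each datapoint could also put early ratings in front of the body that helps decide.

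The SAP seems to add to this. With no visit named and no rule for repeated scores, an early wound rating could be pooled with a later scar rating. If each patient had two scores and these were averaged, a difference present only in the later scar would be diluted. If each patient had one score taken at differing visits, unequal timing between two very small arms could pass for a difference between closures.

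**Working it through.** The plan states no figure to reproduce: there is no alpha, power, margin, standard deviation or effect size. The check is mainly a comparison of the passages.

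**1. The two schedules side by side.**

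| Source | Early visit | Later visit | Stage | Stated use |
|---|---|---|---|---|
| Study Design, stage-two outline | 10 days | 3 months | two | photographs; POSAS described in the same outline |
| Data and Safety Monitoring | week after surgery | six weeks | not named | adverse-event check |

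In days, six weeks = 6 × 7 = 42, and 3 months = 365.25/4 = 91.3. The later visits lie 91.3 − 42 = 49.3 days apart, a ratio of 91.3/42 = 2.17. This would measure a conflict only if both were given as the last visit for the same stage and purpose. The safety plan does not call six weeks the last visit. A patient seen at about a week, at six weeks and at 3 months satisfies both passages. What is shown is an unreconciled difference, not a contradiction.

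**2. Could the stage 1 comparison rest on a wound 7 to 10 days old?** Study Design places it after follow-up, and both schedules contain a later visit. On either schedule the comparison comes after that later visit, so it cannot rest on the first visit alone. Reports to the IRB during follow-up are compatible with a comparison at its end.

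**3. What could the SAP wording do to the summary?** Two mutually exclusive cases:

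- Two scores per patient, averaged with equal weight, with no early difference and a late difference *d*: (0 + *d*)/2 = *d*/2.
- One score per patient from mixed visits, with an early-to-late change *T*: moving one of *n* patients from an early to a late score shifts that arm's mean by *T*/*n*. This is *T*/4 for the planned arm of 4. For an arm of 3 it is *T*/3. An arm of 3 would follow from 7 − 4 = 3 if the 7 enrolled filled one arm; the actual split is not given.

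The documents do not supply *d*, *T*, the number of scores per patient or any averaging rule. An investigator's reply to the IRB office, printed above the SAP, mentions a single post-operative appointment. It is informal, undated as to visit and not SAP text, so it does not settle which case applies, if either does.

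**4. What depends on the answer?** The continuation review form marks all study activities as complete and reports 7 enrolled in total, against 8 planned for stage 1 alone. No available page reports a move to stage two. The SAP describes a pilot with descriptive statistics only, so no error rate or sample size changes with the visit.

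**5. Would a fixed rule help?** Restricting the summary to the last visit would now be a post hoc choice, and it would drop any of the 7 patients without a score at that visit. Showing each score with its visit and days from surgery answers the same question and keeps every patient.

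**The case for a change.** The strongest case for acting starts from the application form, which asks for the timing of procedures and a visit-by-visit listing. The Research Procedures answer gives neither. Assigning the schedules to different stages does not close the gap: if the 10-day and 3-month visits belong to stage two only, stage 1 has no stated time for scar assessment. If they cover both stages, the safety plan's visits still need relating to them. A descriptive mean also needs a defined time point and one value per patient. Closure of the study does not remove the value of knowing whether timing was balanced between the arms.

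Most of this stands as description. The length of stage 1 follow-up is not written in the available text, the two sets of visits are not related to each other, and the SAP names no visit. The schedule may stand elsewhere: the consent pages and the data-collection attachments were not available, and the inclusion criteria speak of intervals as already set.

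What does not stand is the step from an unwritten detail to a faulty plan. No stated rule is shown to give a wrong answer, and the dilution and imbalance arguments need data structures that nothing in the documents shows to have occurred.

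**Conclusion.** This is missing detail that analysts fill sensibly, and it does not call for a change to the plan. The stage 1 comparison is placed after follow-up, the two sets of visits can be kept together, and the SAP is a descriptive account of a closed pilot with 7 patients. No inferential result turns on the choice of visit, and the size of any distortion cannot be derived from the documents.

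Anyone reporting the study will need to reconcile the Study Design and safety-plan visits, say which visit's photographs and surveys the independent group saw, and show POSAS scores by visit. This is ordinary reporting. This review does not choose between the schedules.

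The conclusion rests on two assumptions: that the documents as supplied reflect the study's final status, and that no stage-two comparison was made, which 7 enrolled against 8 planned for stage 1 suggests but does not prove.

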Hi, this question does not apply to our study. There were no results to communicate as there were no tests that were done. This was purely an observational study with a survey that the patient filled out in their postop appointment. I am not sure what the violation is that is being alleged here

Protocol Type Comment by [name] - ORI to IRB/PI on 6/4/2024 3:03:53 PM

Both of the uploaded signed consents are missing checkboxes and initials in the paragraph re: permission to contact participants for return of results or incidental findings (p. 4.). Please submit a violation report for this issue and include the following: 1) Was this missed on all of the signed consents? and 2) Do you anticipate any issues arising from missing this selection? (i.e., how likely is it that there were any incidental findings or results to be returned?) Let me know if you have questions about this request.

Date: March 30, 2025

Identifiers: NCT05981443 Unique Protocol ID: BrowPtosis

Brief An Analysis of Dermabond vs. Non-Absorbable Sutures in Skin Closure for

Title: Brow Ptosis Procedures

Our statistical analysis plan for this pilot study consists of using only data gathered using the POSAS survey administered to patients at their post-operative visits. We used this survey and demographic data to perform basic descriptive statistics to detect if there was a difference between the reported rates of patient satisfaction and ratings of their scars.

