In terms of monetary expenditures, one tube of octyl-2-cyanoacrylate costs approximately \$24. Macario et al site that one minute of operating room time costs approximately \$29, varying in case complexity. We would like to assess the total costs between the two techniques when time in the OR is taken into account.

We hypothesize that the scars will be equivalent in assessment and ultimately be less costly with less patient distress. We also suspect that the skin glue may create an occlusive barrier to infectious contamination of the wounds and potentially a lower complication rate.

Objectives

List your research objectives. Please include a summary of intended research objectives in the box below.

- 1. To determine if octyl-2-cyanoacrylate provides equivalent wound healing compared to conventional non-absorbable skin suture techniques
- 2. To determine if octyl-2-cyanoacrylate provides equivalent scar appearance compared to conventional non-absorbable suture techniques
- 3. To determine the cost effectiveness of the use of octyl-2-cyanoacrylate for skin closure compared to conventional non-absorbable suture techniques
- 4. To determine if octyl-2-cyanoacrylate results in equivalent complication rates compared to conventional non-absorbable suture techniques

Study Design

Describe and explain the study design (e.g., observational, secondary analysis, single/double blind, parallel, crossover, deception, etc.).

- · Clinical Research: Indicate whether subjects will be randomized and whether subjects will receive any placebo.
- Community-Based Participatory Research: If you are conducting community-based participatory research (CBPR), describe
 strategies for involvement of community members in the design and implementation of the study, and dissemination of results from
 the study.
- Qualitative research: Indicate ranges where flexibility is needed, if a fixed interview transcript is not available, describe interview
 topics including the most sensitive potential questions.

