- If you will conduct a record or chart review, list the beginning and end dates of the records you will view.

See attachments for the POSAS survey that will be used to grade scar appearance.

Attachments

Attach Type File Name			
DataCollection 77074_DataCollection_267377.pdf			
DataCollection dss_2017_12_22_patel_ds-00686-2016_sdc1.pdf			

Resources

Describe the availability of the resources and adequacy of the facilities that you will use to perform the research. Such resources may include:

- Staffing and personnel, in terms of availability, number, expertise, and experience;
- Computer or other technological resources, mobile or otherwise, required or created during the conduct of the research;
- Psychological, social, or medical services, including equipment needed to protect subjects, medical monitoring, ancillary care, or counseling or social support services that may be required because of research participation;
- Resources for communication with subjects, such as language translation/interpretation services.

Patient histories, physical examinations, and discussions regarding candidacy for the study will occur in the University of Kentucky Ophthalmology Clinics. The operations will be performed at the University of Kentucky Center for Advanced Surgery. The equipment used to perform the procedure will be in accordance with the usual standard of care for a direct excision brow lift. [name] and the enrolled patient will fill out the described questionnaires. We do not anticipate the need for psychological or social services. We do not anticipate the need for special medical monitoring, ancillary care, equipment needed to protect subject other the usual standards in perioperative and intraoperative care.

Potential Risks & Benefits

Risks

- Describe any potential risks including physical, psychological, social, legal, ability to re-identify subjects, or other risks. Assess
 the seriousness and likelihood of each risk.
- Which risks may affect a subject's willingness to participate in the study?
- · Describe likely adverse effects of drugs, biologics, devices or procedures participants may encounter while in the study.
- Qualitative research describe ethical issues that could arise while conducting research in the field and strategies you may use to handle those situations.
- Describe any steps to mitigate these risks.

Benefits

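### Objective 4 asks whether complication rates are equivalent by closure, but no planned analysis in either stage compares complications between glue and suture

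*Combined protocol and SAP*

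**What the plan says.** The Objectives section lists four aims without assigning any of them to a stage. The fourth reads "To determine if octyl-2-cyanoacrylate results in equivalent complication rates compared to conventional non-absorbable suture techniques".

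The Data and Safety Monitoring section has the principal investigator see patients in the week after surgery and again at six weeks. At these visits the investigator looks for adverse events and specifically for dehiscence, infection and necrosis. Nothing limits these checks to one arm. The same section suspends the study temporarily if dehiscence, necrosis or serious infection occurs in a glue patient. The same events in a suture patient do not suspend it.

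The statistical analysis plan at the end of the document covers the pilot and describes an analysis "using only data gathered using the POSAS survey administered to patients at their post-operative visits". It adds demographic data and basic descriptive statistics "to detect if there was a difference between the reported rates of patient satisfaction and ratings of their scars". Complications are not mentioned. The Data Collection & Research Materials section gives the purpose of the survey: "See attachments for the POSAS survey that will be used to grade scar appearance".

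The stage two outline under Study Design says that complications will be monitored and recorded. It does not say how they will be summarised or compared.

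**The concern.** Equivalence of complication rates is a comparison between two closures, so it needs at least a count in each arm. The plan arranges for the observations, and the analysis plan then shuts them out with the word *only*. That is more than a detail left unsaid.

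Complications are also a stated uncertainty of this trial. The background cites a review that found more dehiscence with one of the closure methods it compared. The hypothesis paragraph suggests that glue may lower the complication rate. A report that gives only similar patient scar scores would leave that question where it was. It could also be taken to mean that the two closures perform alike in general, when complications had not been set side by side.

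**Working it through.** **1. Is there a by-arm comparison anywhere?** Each place where complications or the stage 1 comparison appear:

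- *Statistical analysis plan:* patient survey and demographic data. No complications.
- *Study Design, stage 1:* scar appearance is compared between groups, and "If the difference in appearance is negligible, then we will return to the IRB for approval to advance to stage two". No complication summary.
- *Research Procedures and Data and Safety Monitoring, independent review:* "An independent group comprised of two or more non Study Personnel will review before/after photographs and scar surveys for acceptability". No complication counts are listed in the package.
- *Data and Safety Monitoring, suspension rule:* uses complications, but only those in glue patients. It is a safety stop and does not compare the arms.
- *Study Design, stage two outline:* complications are recorded, with no analysis stated.

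No section supplies a count, rate, interval, test or equivalence margin for complications by closure.

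**2. What could the pilot have shown?** Inputs: 4 + 4 = 8 patients planned (Study Design), and 7 enrolled (Subject Info To-Date). The arm split of the 7 is not given. I assume that neither arm exceeded its planned 4, which leaves 4 glue and 3 suture, or 3 glue and 4 suture. In stage 1 both brows receive the same closure, so the unit of count is the patient.

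With 0 events in n patients, the exact two-sided 95% upper limit is 1 − 0.025^(1/n):

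- n = 4: 1 − 0.025^(1/4) = 60.2%
- n = 3: 1 − 0.025^(1/3) = 70.8%

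With 1 event in 4 patients, the exact 95% interval is 0.6% to 80.6%.

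Two-sided Fisher exact p-values:

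- 4/4 v 0/4: 2/70 = 0.029
- 3/4 v 0/4: 8/56 = 0.14
- 2/4 v 0/4: 0.43
- 4/4 v 0/3: 1/35 = 0.029
- 3/4 v 0/3: 5/35 = 0.14
- 3/3 v 0/4: 1/35 = 0.029

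Under either split, a glue excess with no suture events reaches p < 0.05 only if every glue patient has a complication.

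**3. How far is this from an equivalence claim?** The documents give no complication rate or margin, so these are assumptions. Take equal true rates p in two parallel arms, two one-sided tests at 5% each, and 80% power. Then n per arm = 2p(1 − p)(1.645 + 1.282)² / m², where m is the margin. With m = 10 percentage points, n is 34 for p = 2%, 82 for p = 5% and 155 for p = 10%. Over margins of 5 to 15 points and the same rates, n runs from 15 to 617 per arm, against 4 planned. Stage two is a within-patient design, so these figures do not size it.

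**The case against.** The strongest reply is that the analysis plan is labelled as the plan for a pilot, while the objectives belong to the whole two-stage project. Study Design gives scar appearance as the stage 1 comparison, and the monitoring section describes phase one as a study of scar phenotype. Closure timing and costing for objective 3 appear only in the stage two outline, which suggests that not every objective was meant for the pilot. This reading is plausible, and it is why I do not call the plan self-contradictory. But no sentence defers objective 4, and the stage two outline contains no complication analysis either. The gap remains on both readings.

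A second reply is that seven patients could not have answered the question. That is right, and it limits the remedy to description.

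Three stronger readings are tempting, and the documents do not support them:

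- *Complications had no bearing on the move to stage two.* The stated trigger is scar appearance, but a glue-arm event can suspend the study. Phase 1 results go to the IRB as they are collected, and the IRB helps decide whether to proceed. Complications could therefore have blocked stage two.
- *Safety oversight was deficient.* The same provisions, with the adverse event summary requested at continuing review, are oversight. The gap is in analysis.
- *Objective 1, on wound healing, is also unanalysed.* Wound healing is not defined, and the contents of the two data collection attachments are not available, so this cannot be settled.

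**Conclusion.** The point holds as a minor one. Objective 4 is a between-closure comparison, the stage 1 checks would supply the data, and neither the analysis plan nor any other section compares complications by arm. All study activities are recorded as complete, so under the plan as written the objective stays unaddressed.

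The size of the gap is one missing descriptive comparison in at most seven patients. It could not have supported equivalence: an arm with no events is still compatible with a true rate of 60.2% or 70.8%, depending on its size. These limits rest on the assumed 4-and-3 split and on every patient having been assessed. The documents confirm neither. The equivalence sample sizes rest on assumed rates and margins, and serve only to show scale.

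**What to change.** In the pilot report, add one table of complications by arm from the one-week and six-week checks: dehiscence, infection, necrosis and any skin reaction noted. Give patient counts over the number assessed, with exact 95% intervals and no test. Add a sentence saying that the pilot does not establish equivalence of complication rates. If objective 4 was always meant for stage two, say that as well.

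In any stage two request or successor protocol, have the analysis plan name complications by closure as the outcome for objective 4 and state how they will be summarised.

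This needs no new patients, visits or staff, provided that the planned checks were recorded. The cost is a little extra reporting. The conclusion would then be limited to patient-rated scars, with wide complication intervals on show.
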